#### Secondary Endpoints

Secondary efficacy endpoints will be analyzed as follows:

- For time to first PE, the survival curves will be compared between the brensocatib dose and placebo using a Cox proportional hazards model based on the ITT Analysis Set. The covariate will include the stratification factors used for the randomization.
- For the proportion of subjects who are exacerbation free, the comparison between brensocatib and placebo will be analyzed using logistic regression with treatment group and randomization stratification factors as fixed effects.
- Absolute change from Baseline in postbronchodilator FEV1 will be analyzed using a linear repeated measures model with fixed effects of treatment, stratification factors, visit, treatment-by-visit interaction, as well as the continuous, fixed covariate of Baseline value. An unstructured variance-covariance matrix will be fit.

IND Number:	133790
EudraCT Number:	2020-003688-25

- The rate of severe PEs will be analyzed using the same method as the primary endpoint.
- The change from Baseline in QOL-B Respiratory Symptoms Domain Scores in the adult population will be analyzed using a linear repeated measures model with fixed effects of treatment, stratification factors, visit, treatment-by-visit interaction, as well as the continuous, fixed covariate of Baseline value. The variance-covariance structure will be compound symmetric with the robust sandwich variance estimator

Safety endpoints including incidence and severity of treatment-emergent adverse events, clinical laboratory test results, vital signs, and electrocardiogram (ECG) will be descriptively summarized by treatment.

Brensocatib concentration data will be listed and summarized by dose level over each scheduled sampling time using descriptive statistics. Individual plasma concentration data versus time will be listed. Individual and geometric mean plasma concentration-time data will be graphically displayed.

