## 1.7.3. Regulatory Compliance

The study protocol, subject information and consent form, adolescent assent form (if required per local requirements), the Investigator brochure, any subject diary card or written instructions to be given to the subject, available safety information, subject recruitment procedures (eg, advertisements), information about payments and compensation available to the subjects and documentation evidencing the Investigator's qualifications should be submitted to the IRB/EC for ethical review and approval according to local regulations, prior to the study start. The written approval should identify all documents reviewed by name and version.

Changes in the conduct of the study or planned analysis will be documented in a protocol amendment and/or the SAP.

All protocol amendments and changes to the ICFs and assent form (if required per local requirements) or changes of the investigational site, facilities, or personnel (when applicable) must be submitted to the IRB/EC (and the health authority, if applicable), and where necessary, approval from the IRB/EC (and the health authority, if applicable) must be obtained. The Investigator should notify the IRB/EC of deviations from the protocol or SAEs occurring at the site and other AE reports received from the Sponsor, in accordance with local procedures.

As required by local regulations, the Sponsor's local Regulatory Affairs group will ensure all legal aspects are covered, and approval of the appropriate regulatory bodies obtained, prior to study initiation, and that implementation of changes to the initial protocol and other relevant study documents happen only after the appropriate notification of or approval by the relevant regulatory bodies.

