## 10.4.6.2. Analysis of Secondary Efficacy Endpoints

## 10.4.6.2.1. Main Analysis of Secondary Efficacy Endpoints

All inferential analyses for PE-related endpoints will be based on PEs that have been confirmed through the adjudication process. The primary estimand for the secondary endpoints will be On-Study estimand in which all observed data (ITT Analysis Set) will be included in the analysis.

- For time to first PE, the survival curves will be compared between the brensocatib dose and placebo using a Cox proportional hazards model based on the ITT Analysis Set. The covariate will include the stratification factors used for the randomization (see Section 10.4.6.1).
- For the proportion of subjects who are exacerbation free, the comparison between brensocatib and placebo will be analyzed using logistic regression with treatment group and randomization stratification factors as fixed effects.

- Absolute change from Baseline in postbronchodilator FEV1 will be analyzed using linear repeated measures model with fixed effects of treatment, stratification factors as noted above, visit, treatment-by-visit interaction, as well as the continuous, fixed covariate of Baseline value. An unstructured variance-covariance matrix will be fit.
- Rate of severe PEs will be analyzed using the same method as the primary endpoint.
- Change from Baseline in the QOL-B Respiratory Symptoms Domain scores will be
  analyzed using linear repeated measures model with fixed effects of treatment,
  stratification factors, visit, treatment-by-visit interaction, as well as the continuous,
  fixed covariate of Baseline value. The variance-covariance structure will be
  compound symmetric with the robust sandwich variance estimator. The subgroup of
  adult subjects will be included in the analysis because the QOL-B is completed by
  adult subjects only.

Further analysis details and sensitivity analyses as well as supplementary analyses for secondary endpoints will be described in the SAP.

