## 1. INTRODUCTION

The purpose of this Statistical Analysis Plan (SAP) is to describe the planned analyses to be included in the Clinical Study Report (CSR) for study INS1007-301.

The reader is encouraged to read the study protocol for details on the conduct of this study, the operational aspects of clinical assessments, and the timing for a participant to complete the participation in this study.

The SAP is intended to be aligned with the protocol. However, the SAP may contain more details or other types of analyses. Differences in descriptions or explanations provided in the study protocol and this SAP, are discussed in Section 13. The SAP is based upon the following documents:

- Clinical Study Protocol (CSP) (Global) Amendment 4, Version 7, dated 13 Feb 2024,
- Electronic Case Report Form (eCRF) Version 14, dated 21 Sep 2023.

Details pertaining to the scope of analyses for Data Monitoring Committee (DMC) review are provided in the DMC SAP.

The analyses described in this plan are considered a priori, in that they have been defined prior to database lock and unblinding. Any analyses not described herein performed subsequent to unblinding will be considered post hoc and exploratory.

CONFIDENTIAL Page 12 of 139

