#### 8.3.3.1. Main Analyses

The Main Estimand of the change from baseline in post-bronchodilator FEV1 (L) at Week 52 is the On-Study Estimand in which all observed data will be included in the analysis (see Section 2). The ITT Analysis Set (see Section 5.2) will be used for this Estimand. The derivation of the endpoint is detailed in Section 6.7.3. Tabulations described below will not be limited to Week 52 but summarize all scheduled time points.

Pre- and post-bronchodilator FEV1 assessments at baseline and Weeks 16, 28, 40, 52 will be summarized by treatment group using descriptive statistics. The summary will include changes from baseline, too.

Change from baseline in post-bronchodilator FEV1 (L) will be analyzed using a linear repeated measures model including treatment group, visit, treatment-by-visit interaction, sputum sample being classified as positive or negative for *Pseudomonas aeruginosa* at Screening Visit, the number of prior PEs [<3 or  $\ge$ 3] in the previous 12 months, stratification region (North America, Europe, Japan, and the Rest of the World), and age group (adult, adolescent) as fixed effects, and baseline value as covariate. The variance-covariance structure will be compound symmetric with the robust sandwich variance estimator (option EMPIRICAL in the PROC-Statement). This analysis will be performed in SAS using MIXED procedure. The OM option will be used to adjust the coefficients for the LSMEANS to reflect the observed data.

If the age group covariate creates estimability issues, it may be removed. If the model still does not converge after removing the age group covariate, other handling including using the parametric covariance estimator instead of the robust sandwich covariance estimator may be applied. When using the parametric covariance estimator, the restricted maximum likelihood (REML) estimator will be applied, with the variance-covariance structure being applied with the following sequence: UN -> TOEPH -> ARH(1) -> CSH. If the model still does not converge, the maximum likelihood estimator will be applied instead of the REML estimator, with the same sequence of the possible variance-covariance structures. The adjustment will be added to the footnote of the corresponding outputs.

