#### 8.3.5.1. Main Analyses

The Main Estimand of the change from baseline in QoL-B Respiratory Symptoms Domain Score at Week 52 is the On-Study Estimand in which all observed data will be included in the analysis (see Section 2). The population attribute for this Estimand is adult participants with NCFBE who meet all inclusion criteria and none of the exclusion criteria. The ITT Analysis Set (see Section 5.2) will be used for this Estimand.

Calculated Respiratory Symptoms score (items 29 to 37) will be summarized at baseline and change from baseline at Week 52 by treatment group using descriptive statistics. Single item responses (each question) will be summarized by treatment group in a shift table. Completion rates will be presented by time point (see Section 6.7.5.10).

Change from baseline of calculated Respiratory Symptoms score (items 29 to 37) at Week 52 will be analyzed using a linear repeated measures model including treatment group, visit, treatment-by-visit interaction, sputum sample being classified as positive or negative for *Pseudomonas aeruginosa* at Screening Visit, the number of prior PEs [<3, ≥3] in the previous 12 months and stratification region (North America, Europe, Japan, and the Rest of the World) as fixed effects, and baseline value as covariate. Given that the QoL-B will be administered every two weeks for a total of 26 time points, estimation of a complex variance-covariance structure with many parameters will be untenable. Therefore, the variance-covariance structure will be compound symmetric with the robust sandwich variance

CONFIDENTIAL Page 62 of 139

estimator. Results will be presented in the same manner as the analysis of "Change from Baseline in Post-bronchodilator FEV1 (L) at Week 52" (see Section 8.3.3), including a figure displaying the adjusted means and corresponding 95% confidence intervals at Week 52 by treatment group. The OM option will be used to adjust the co-efficients for the LSMEANS to reflect the observed data. The between-treatment differences and corresponding 95% CIs will be presented; the associated p-value for the adjusted mean difference will be compared to the appropriate alpha level per the multiple test procedure.

If the model fails to achieve convergence, similar handling described in Section 8.3.1.1 Main analysis for Change from Baseline in Post-bronchodilator FEV1 (L) at Week 52 will be applied and the adjustment will be added to the footnote of the corresponding outputs.

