### 13. CHANGES TO PROTOCOL-PLANNED ANALYSES

### • ITT Analysis Set:

### CSP, Section 10.2.2

The ITT Analysis Set comprises all subjects who were randomized subjects. This set will be analyzed using the treatment to which the subject was randomized, regardless of the treatment actually received.

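### The SAP models the alpha-controlled FEV1 Week 52 tests (H7, H8) with compound symmetry where the protocol specifies an unstructured matrix; Section 13 omits the change, and the only reason given does not fit four visits

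*SAP*

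**What the plan says.** Protocol 10.4.6.2.1 says of the FEV1 repeated-measures model: "An unstructured variance-covariance matrix will be fit". The synopsis says the same. For QoL-B both places give a different structure: "The variance-covariance structure will be compound symmetric with the robust sandwich variance estimator". The protocol therefore treats the two endpoints differently.

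SAP 8.3.3.1 gives FEV1 the QoL-B structure: "The variance-covariance structure will be compound symmetric with the robust sandwich variance estimator (option EMPIRICAL in the PROC-Statement". Appendix I agrees: the Step 5 code has TYPE=CS with METHOD=REML and EMPIRICAL, and the FEV1 main-analysis entry says the same code is used without the BY statement. The unstructured matrix survives only as a fallback, after non-convergence and a switch to the parametric estimator, "with the variance-covariance structure being applied with the following sequence: UN -> TOEPH -> ARH(1) -> CSH".

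The SAP's only argument for compound symmetry is in the QoL-B section (8.3.5.1): "Given that the QoL-B will be administered every two weeks for a total of 26 time points", a richer structure is judged unworkable.

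On documentation, protocol 1.7.3 says: "Changes in the conduct of the study or planned analysis will be documented in a protocol amendment and/or the SAP". SAP Section 1 says: "Differences in descriptions or explanations provided in the study protocol and this SAP, are discussed in Section 13". That section, "CHANGES TO PROTOCOL-PLANNED ANALYSES", covers the ITT, PD and PK analysis sets, wording of exploratory endpoints, concomitant procedures and medical history. The FEV1 covariance structure is not there.

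**The concern.** FEV1 at Week 52 is Family 4 of the gatekeeping procedure (SAP 6.3.1) and, within a dose, stands in front of Families 5 and 6. Its p-value is compared with the procedure's alpha, so protocol and SAP should name the same model, or the SAP should record the change and the reason.

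The choice matters because some Week 52 values will be missing through study withdrawal, missed visits, tracings not accepted for analysis (SAP 6.7.3) or early end-of-treatment data excluded under SAP 6.4.9. A likelihood-based model fills those gaps implicitly from earlier visits, and the working covariance sets the weights. A sandwich estimator gives a valid standard error for whatever quantity is being estimated; it does not move the estimate back if the weights are wrong.

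The prespecified check is also conditional. The zero-delta cell of the tipping-point analysis (SAP 8.3.3.2, Appendix I) largely avoids reliance on compound symmetry, because it analyses data completed by imputation. SAP 6.2 runs it only after a significant main result. After a non-significant one, the slope model in 8.5.11 remains, and it does not estimate the Week 52 contrast.

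**Working it through.** **1. Does the QoL-B reason carry over?** An unstructured matrix for T visits has T(T+1)/2 parameters; compound symmetry has 2.
- QoL-B: 52/2 = 26 time points, as the SAP states; 26 × 27/2 = 351.
- FEV1: Weeks 16, 28, 40 and 52, so T = 4; 4 × 5/2 = 10.

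Ten parameters at about 540 per arm is unproblematic, and the SAP itself puts the unstructured matrix first among its fallbacks. As written, a 2-parameter model that fails to converge would be replaced by a 10-parameter one.

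**2. When does the structure change the estimate?** Take one dropout time, with proportion d missing Week 52 in an arm. Let g be the dropouts' mean deviation from the arm mean at earlier visits, b_true the correct regression of Week 52 on those visits, and b_work the one implied by the fitted covariance. Under missing at random the error in that arm's Week 52 mean is

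d/(1−d) × (b_work − b_true) × g.

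If arms share the covariance and the dropout rule, the error is equal in each arm and cancels from the contrast. If the rule differs by arm, it does not cancel unless b_work = b_true. A pooled unstructured matrix gives b_work = b_true only if the covariance is the same in all arms; otherwise it too leaves an error.

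**3. Size.** The documents give no FEV1 SD, correlation, dropout rate or power figure, so there is no plan figure to reproduce and every input below is assumed: AR(1) correlation 0.6 to 0.9 per visit, residual SD 0.25 L constant or rising from 0.20 to 0.26 L, 5% dropout per interval after visits 1 to 3 (1 − 0.95³ = 14.3%), and no true effect. Large-sample fits (1,000,000 per arm, equal covariances) give compound symmetry minus unstructured at Week 52, in mL, for correlations 0.6/0.7/0.8/0.9:

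| Log-odds of dropout per SD of last FEV1, by arm | Constant SD | Rising SD |
|---|---|---|
| same in both | at most 0.07 in size | at most 0.07 in size |
| −1 and −0.75 | +0.55/+0.53/+0.50/+0.21 | −0.09/−0.20/−0.57/−0.88 |
| −1 and −0.5 | +1.33/+1.20/+1.00/+0.62 | −0.16/−0.55/−1.22/−1.96 |
| −1 in placebo only | +2.95/+2.75/+2.18/+1.31 | −0.22/−1.14/−2.57/−4.35 |

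The unstructured fit stayed within 0.83 mL of the truth (Monte Carlo SE about 0.4 mL). Other fits with dropout rules differing by arm reached 5.0 mL at 11 to 16% dropout. At 540 per arm the SD of the estimate is 16.2 to 18.5 mL unstructured and 16.1 to 18.4 mL under compound symmetry, so 5 mL is 5/18.4 = 0.27 to 5/16.1 = 0.31 standard errors. A 0.28 SE shift turns a two-sided 5% test into 5.9%, and 2.5% (the Bonferroni share per dose) into 3.1%.

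**4. Rejection rates.** Three arms of 540, 5,004 null trials per scenario, two-sided 5%, both contrasts, sandwich SE in both models (Monte Carlo SE 0.3 points):

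| Scenario | Compound symmetry | Unstructured |
|---|---|---|
| correlation 0.9, rising SD, same rule | 5.0/4.7 | 5.0/4.8 |
| same, −1 and −0.5 | 5.4/4.9 | 4.8/4.7 |
| same, placebo only | 6.1/6.1 | 5.0/5.2 |
| correlation 0.6, constant SD, placebo only | 5.3/5.2 | 4.9/4.6 |

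A second, smaller set (300 replicates, dropout 11 to 27%) shows how far this depends on the inputs. With outcome driving dropout in opposite directions in the two arms, the gap was 3.4 to 6.4 mL at 14% dropout and 6.7 to 12.8 mL at 27%. Rejection under compound symmetry reached 0.113 in the most extreme cell, against 0.053 unstructured.

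**5. Unequal covariances.** Constant SD, same dropout rule in both arms, about 14% dropout. Correlation 0.85 in one arm and 0.70 in the other: bias about 7.5 mL unstructured, 5.5 mL compound symmetry. Correlation 0.9 and 0.6: 14.0 and 10.7 mL. With SD 20% larger in one arm (correlation 0.8, rising SD) the order reverses: 0.1 mL unstructured, 1.3 mL compound symmetry.

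**The case against.** Compound symmetry with the sandwich estimator is stated openly in 8.3.3.1 before unblinding, and protocol 1.7.3 lets the SAP document a changed analysis. That stands. A reader might infer an impermissible or concealed change, and the documents do not support that. What is missing is the Section 13 entry that the SAP promises, and a reason.

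The numerical effect is small in most scenarios. That also stands. Data are collected after discontinuation of study drug (SAP 6.6), which limits missingness, and the structures agree when arms share one covariance and one dropout rule.

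The unstructured matrix is not uniformly safer. The Step 5 code has no arm-specific covariance, so changing its TYPE gives a matrix pooled over arms. That needs missing at random, a correct mean model and equal covariances; step 5 of the working shows cases where it does worse. A reader might infer that the protocol's model is unbiased and the SAP's is not, which does not follow.

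Nor does TYPE=UN alone return the SAP to the protocol. The protocol names no sandwich estimator for FEV1 and does not list age group in that model. The SAP has both, and Section 13 mentions neither.

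**Conclusion.** The point holds as an unlisted and unexplained change of model for an alpha-controlled endpoint. Protocol and SAP name different covariance structures for H7 and H8, and the SAP's one argument for its choice concerns 26 time points, not four. Compound symmetry adds an assumption to the Week 52 estimate that the sandwich does not remove, and it buys no useful precision.

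With equal covariances across arms, the difference is about zero under a common dropout rule. It is a few mL, up to about 5 mL in either direction, at about 14% dropout when outcome drives dropout in one arm only. Larger values need heavier or opposing dropout. These are scenarios on assumed inputs, not bounds, and the sign in this trial cannot be told from the documents. A reader might infer that the type I error of H7 and H8 is materially inflated; the documents give no inputs that would support this, and it is not claimed.

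**What to change.** In SAP 8.3.3.1 and Appendix I Step 5, make TYPE=UN the main FEV1 structure. On non-convergence use the SAP's own remaining sequence (TOEPH, ARH(1), CSH), stating at each step whether EMPIRICAL is kept. Keeping it is worthwhile: with SD 20% larger in one active arm, unstructured fits with model-based standard errors rejected 3.3% and 5.9% for the two contrasts, against 5.2% and 5.1% with EMPIRICAL. List in Section 13 what still differs from the protocol's FEV1 model: EMPIRICAL and the age-group covariate.

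If compound symmetry is kept, add a Section 13 entry with a reason that fits four visits, and prespecify the unstructured model as a sensitivity analysis for H7 and H8, run whatever the main result.

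The cost is SAP wording and one code option before database lock, with no new data. The main model gains 8 covariance parameters (10 instead of 2), negligible at about 540 per arm. In the repeat in about 40 adolescents (SAP 8.3.6) the fallback may be needed. Keeping compound symmetry costs one entry and one extra model run.

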#### 8.3.3.2. Sensitivity Analyses

A tipping point analysis will be used to investigate the impact of missing data and to examine the robustness of the main analysis. The tipping point will be identified when the respective comparison is no longer statistically significant at two-sided  $\alpha$ = 0.05.

To explore the impact of missing data on the mean treatment effect, different assumptions of the effect will be evaluated by adding an additional penalty (delta) prior to analyzing the imputed datasets and combining the results. For each brensocatib dose comparison relative to placebo, the tipping point penalties (delta adjustment) will be applied in a bi-directional manner. The deltas or delta adjustments are pre-selected multiples of the observed treatment effect. If the observed mean treatment effect from the main analysis is x, the deltas to be investigated will range from -3\*x to 0 for the active arm, in increments of 10 mL. The delta adjustments to be applied to the imputed data in placebo arm will range from 0 to 3\*x. The increment or range may be refined based on the analysis results and the location of the tipping point.

All recorded data up to and including the Week 52 assessment (see Section 2) will be included. Missing data will be imputed using multiple imputation first based on the MAR mechanism. The imputation model will contain the same covariates as in the main analysis model (see Section 8.3.3.1). 100 separate complete data sets for each comparison within the pre-selected delta range will be generated and analyzed. Markov Chain Monte Carlo (MCMC) method will be used to fill intermittent missing values, e.g., missing values between reported visits, under the assumption of MAR, resulting in an intermediate data with monotone missing patterns. MCMC will use a separate chain for each imputation (multiple chains), a non-informative prior for the means and covariances, and 200 burn-in iterations before the very first imputation in each chain. For monotone missing data the regression method will be applied using a separate regression for each of the non-monotone imputed datasets. Results will be combined across imputations using Rubin's method (Rubin 1987). The relevant delta decrement grid for each brensocatib dose vs. placebo comparison will be populated with the corresponding p-value.

Technical details for the implementation in SAS can be found in Appendix I.

